Pressure ulcers require significant costs on both the health care system and patients [5]. In addition to the gangrene and cellulite-related pain and suffering, these wounds have the potential to result in amputation, diminished quality of life, and even death [6]. Pressure ulcers can be treated in a number of ways, including wound cleaning, debridement, improved dressings, patient optimization, antibiotics, and reconstructive surgery. Additionally, more recent alternatives for treatment are offered, including cell therapy, hyperbaric oxygen therapy, and negative pressure wound therapy [7].

Pressure ulcers have been treated in China using traditional Chinese remedies such as herbal medicinal ointments, particularly Moist Exposed Burn Ointment (MEBO), acupuncture, and moxibustion [8–10]. MEBO was successfully used to treat burns in clinical settings in earlier investigations. It consists of sesame oil, b-sitosterol, berberine, and other Chinese herbal plant ingredients [11].

Additional clinical and experimental research has revealed that MEBO not only has analgesic and antibacterial benefits but can also hasten the healing process for burn wound patients [12–15]. Additionally, it can either promote debridement and epithelial repair or lower treatment expenses for patients and their families [11,16]. MEBO has also reportedly been shown to aid in the healing of neurogenic and chronic ischemic ulcers [12,15].

- 2 -

Short Title: Impact of using Zinc Oxide versus Moist Exposed Wound Ointment (MEBO) in treatment of second stage pressure ulcer: A randomized control clinical trial.

Version: 5.0 (Dated 28-Mar-2023)

Effective date: 29-Mar-2023

Expiration date: 29-Mar-2024

Impact of using zinc oxide versus Moist Exposed Wound Ointment (MEBO) in treatment of second stage pressure ulcer: A randomized control clinical trial.

Topical zinc oxide aids in the re-epithelialization process, which is important for wound healing. Clinical research has shown that people with low zinc levels had slower healing of ulcers [17], and zinc can be administered topically or orally to help these patients recover more quickly [18].

The incidence of PU is still very high despite established risk factors and the attentiveness of healthcare professionals. In the range of 22.5% to 66.6% of patients, PU develops at some point during prolonged hospitalization. Each patient's ulcer costs around 1.71-470.49 Euros per day to treat, depending on the context. Although there are many different dressings and topical medications available, none has been proven to be better than the others [19-21].

To our knowledge, no study exists in the literature comparing the effects of local application of mebo and oxide zinc ointment in treatment of stage II pressure ulcer. Therefore, the present study was designed to compare the effects of zinc oxide versus MEBO in treatment of second stage pressure ulcer.

Significance of the study

Pressure Ulcers are associated with decreased quality of life and increased morbidity, mortality, and cost. A systematic review found that the cost of PU treatment varied from 1.7 to 470.5 € per patient per day across different settings. Additionally, PUs may cause emotional distress to patients and their families and frequently lead to their dissatisfaction with the health-care system and mistrust of the health-care providers [22].

Pressure ulcer risk assessment, prevention and management are important to reduce PU burden in ICU patients. Comprehensive evidence-based guidelines on PU prevention and care were recently updated. However, clinical studies about this topic are uncommon and mostly of low-to-moderate

Impact of using zinc oxide versus Moist Exposed Wound Ointment (MEBO) in treatment of second stage pressure ulcer: A randomized control clinical trial.

quality. They emphasize the need for a multifaceted care approach and multidisciplinary involvement [23.24].

Globally, the incidence of pressure ulcers varied from 2 - 20 ulcer/1000 patient-days, depending on the institution and the population of patients studied. Also, the prevalence varied from 5-13% [25-27]. Nationally a study done by Al-Hashemi (2019) at King Abdulaziz Medical City (KAMC) – Jeddah-Saudi Arabia revealed that the calculated incidence 1.6 ulcer/1000 patient-days and prevalence 5.7% in this study is very close to the figures published in the literature previously [28].

A network meta-analysis (2017) about dressings and topical agents for treating pressure ulcers (Review) of data from 39 studies (evaluating 21 dressings and topical agents for pressure ulcers) concluded that consequently we are unable to determine which dressings or topical agents are the most likely to heal pressure ulcers and more research is needed to determine whether particular dressings or topical agents improve the probability of healing of pressure ulcers [29]. Moreover Boyko et al. (2018), in a review of the current management of pressure ulcers, stated that despite many treatments available, none of them is superior to the other, and pressure ulcers remain a debilitating and costly issue. They recommended additional research to develop products more effective in preventing and treating pressure ulcers [20].

The incidence of pressure ulcers will possibly grow rapidly in the future due to increased life expectancy and aging. However, although various methods are used to treat pressure ulcers, no standard therapy has previously been established. After searching the literature there no studies done before to compare the effects of zinc oxide versus MEBO in treatment of second stage pressure ulcer and because there is no standardization for this practice this clinical trial will be conducted to compare the effects of zinc oxide versus MEBO in treatment of second stage pressure ulcer and determine which one is superior to other.

OBJECTIVES:

The **primary objective** of this study is to:

- 4 -

Short Title: Impact of using Zinc Oxide versus Moist Exposed Wound Ointment (MEBO) in treatment of second stage pressure ulcer: A randomized control clinical trial.

Version: 5.0 (Dated 28-Mar-2023)

Effective date: 29-Mar-2023

Expiration date: 29-Mar-2024

Impact of using zinc oxide versus Moist Exposed Wound Ointment (MEBO) in treatment of second stage pressure ulcer: A randomized control clinical trial.

- To evaluate the efficacy of using zinc oxide versus moist exposed wound ointment in treatment of second stage pressure ulcer.

Secondary Objectives

- To determine the recovery time for both ointments.

Objective measures

For the primary objective

Wound healing will be assessed by using Bates–Jensen Wound Assessment Tool (BWAT) daily for both treatments.

For the secondary objective

The duration of treatment will be record at the assessment sheet so Recovery time will be determined from this sheet.

Research Design:

- Open label randomized control clinical trial study with a pilot study-using questionnaire.

Inclusion Criteria:

- Subjects ≥ 18
- Willing to participate.
- KAMC cases in medical ward, neuroscience ward, and intensive care unit.
- Newly cases diagnosed with second stage pressure ulcer according to the European pressure ulcer advisory panel/national pressure ulcer advisory panel (NPUAP) guidelines.

Exclusion Criteria:

- 5 -

Short Title: Impact of using Zinc Oxide versus Moist Exposed Wound Ointment (MEBO) in treatment of second stage pressure ulcer: A randomized control clinical trial.

Version: 5.0 (Dated 28-Mar-2023)

Effective date: 29-Mar-2023

Expiration date: 29-Mar-2024

Impact of using zinc oxide versus Moist Exposed Wound Ointment (MEBO) in treatment of second stage pressure ulcer: A randomized control clinical trial.

- Subjects under 18
- Not consenting to participate
- Patients with suspected hypersensitivity reactions to any of the topical formulation's ingredients.
- Either a category III or IV pressure ulcer.
- Evidence of deep tissue injury (exudative drainage, purple or maroon localized area of discolored intact skin or blood-filled blister due to pressure damage).
- Signs of wound infection (pus draining from the ulcer, a foul-smelling odour, tenderness, heat and increased redness in the surrounding skin and fever).
- Patients who undertaking other therapies that could affect healing, such as corticosteroids, radiation therapy, or chemotherapy for cancer.
- Heavy smoking (more than 20 cigarettes a day).
- Concomitant chronic disease (e.g., diabetes mellitus or frank vascular disease such as Buerger's disease).
- Patients who unable to continue the study because of death, discharge, or change in the care setting.

Randomization

Simple randomization method will be used through electronic randomization. The randomization list was generated electronically through R using the Random Allocation Rule by research center member who did not directly participate in trial recruitment and enrolment. Research center member will define

- 6 -

Short Title: Impact of using Zinc Oxide versus Moist Exposed Wound Ointment (MEBO) in treatment of second stage pressure ulcer: A randomized control clinical trial.

Version: 5.0 (Dated 28-Mar-2023)

Effective date: 29-Mar-2023

Expiration date: 29-Mar-2024

Impact of using zinc oxide versus Moist Exposed Wound Ointment (MEBO) in treatment of second stage pressure ulcer: A randomized control clinical trial.

the participant for this concealment. Allocation sequence will be generated, and the oblique envelopes will be created with the sequence in it and each envelop only open after patient consented and enrolled in the study to determine which treatment the participant will receive.

Blinding

Open label study as True blinding for patients and the research nurse who will apply the topical agent will be difficult as there is a significant difference among the two treatment methods in presentation, colour, density, and odour. the author who will enroll the patients to the study will be blind to treatment assignment. To maintain the blinded status on assessment of outcomes, outcome assessors will be also blinded to treatment allocation.

Study Procedure:

After getting official permission from KAMC IRB, the subject will be randomized using electronic randomization 1:1 ratio. The randomization list was generated electronically through R using the Random Allocation Rule. The data will be collected using Assessment sheet of patient with second stage pressure ulcer tool. Patients will equally be allocated into 2 groups randomly. The zinc oxide group will receive topical zinc oxide twice every 12 hours daily and patients in the MEBO group will receive topical MEBO ointment twice every 12 daily.

The research nurse will be instructed on how to apply the ointment on different surface areas (into and around the edge of ulcers) according to the fingertip unit (FTU). One FTU contains approximately 0.5 g of the ointment. Amounts that were applied to different parts were 7 FTUs for back, 3 FTUs for 1 arm, 1 FTU for both sides of 1 hand, 6 FTUs for 1 leg, and 2 FTUs for 1 foot. The number

Impact of using zinc oxide versus Moist Exposed Wound Ointment (MEBO) in treatment of second stage pressure ulcer: A randomized control clinical trial.

of FTUs applied will be altered by the size of the ulcer. For example, if the patient has a large ulcer on the heel, more ointment was applied in comparison to a small ulcer on a patient's back. For infection prevention, povidone iodine will be used to clean pressure ulcers before MEBO or zinc oxide intervention. Then, the pressure ulcers will be cleansed with normal saline gauze. MEBO will be smeared successively onto the wounds at a thickness of 1mm twice daily with a sterile gloved finger. The same application will be used as for zinc oxide ointment.

Furthermore, removal of the possible causal factors (pressure, shear, and friction) and control of the related general condition (such as nutrition, cleaning of the wound, and management of comorbid disease and other medical factors such as blood sugar level that might interfere with the healing process) will be considered for all patients as standard of care.

To eliminate the possible complicating factor of treatment interactions, all patients in both groups will receive position change every 2 hours, and mattress that helps to protect the vulnerable skin. If a patient has more than one ulcer, all the ulcers will be treated by the same method of cleansing, applying and changing positions and the same treatment.

Patient will be examined daily till complete healing for the pressure ulcer and maximum one month as it was reported by Li et al. (2017) reported that the use of MEBO for one week did not significantly affect the improvement of pressure ulcer grades [29]. Moreover, a study done by Palese 2015 reported that to achieve complete re-epithelialization in Stage II PUs, it takes approximately 23 days. This is quite a long time if we consider that pressures of only 60 to 70 mm Hg for between 30 and 240 minutes are needed to cause tissue damage. On average, a small ulcer heals 12 days faster compared with those with a surface of 3.1 cm² or greater [30] so patient will follow for maximum one month. If

Impact of using zinc oxide versus Moist Exposed Wound Ointment (MEBO) in treatment of second stage pressure ulcer: A randomized control clinical trial.

the pressure ulcer not healed within the month of the treatment duration this patient will return to routine care of the hospital. If the any patient will be unable to continue the study because of death, discharge, or change in the care setting the researcher will be excluded from the study.

Pilot study:

It will conduct before data collection on 10% of patients to explore feasibility for future RCT, the efficiency, internal validity and fundamentally, the delivery of proposed trial and identify barriers and facilitators. Zinc oxide will be applied to 4 patients twice daily and MEBO will be applied to 4 patients twice daily till complete healing for the pressure ulcer and maximum one month. The study' tool will be tested, and these patients will be excluded from the study, after completion the patient will have routine care for pressure ulcer treatment.

Sample Size calculation:

The sample size for the study calculated using the following formula based on the study of Li et al (2017).

$$\text{Sample size (n)} = \frac{p_1(1-p_1) + p_2(1-p_2)}{(p_1-p_2)^2} * C$$

n = Sample size for one group that we need to find out

p1 and p2 = Proportion of two groups

C = Standard value for the corresponding level of α and β selected for the study $(0.84+1.96)^2$.

- 9 -

Short Title: Impact of using Zinc Oxide versus Moist Exposed Wound Ointment (MEBO) in treatment of second stage pressure ulcer: A randomized control clinical trial.

Version: 5.0 (Dated 28-Mar-2023)

Effective date: 29-Mar-2023

Expiration date: 29-Mar-2024

Impact of using zinc oxide versus Moist Exposed Wound Ointment (MEBO) in treatment of second stage pressure ulcer: A randomized control clinical trial.

$n= 0.5 (1-0.5) + 0.167 (1-0.167) (0.84+1.96)^2 / (0.5-0.167)^2 = 27.5 \approx 28$ patients, in addition to attrition rate 20 % therefore sample size will be 34 patients for each group.

A total number 76 patients will be included in the study. A number of eight participants will be included in the pilot study which will equal 10% of the total study number and will be excluded from the study.

Duration of the Study: 12 months in total. The enrolment will be for six months. Follow up will be for maximum 1 months for each subject. A period of 6 months will be for analysis and closing.

Setting:

This study will be carried out at medical ward, neuroscience ward, and intensive care unit at King Abdullah Medical City, Holy Makkah.

Data Collection and Management:

After the official approval from KAMC IRB and the local authority approval. The principal investigator will have a meeting with the team for study implementation overview to ensure the quality and compliance. Researcher will explain the study to the participants and take written consent if they want to participate. For unconscious patient written approval will be taken from there Legally Acceptable Representative. The participation will be voluntary and anonymously. In case of passing away the collected data will not be used and safety reports will be submitted as per the local gaudiness. In case of discharge the collected data will not be used and the patient will be excluded. All data collection sheets will be kept in a locked file cabinet with the researchers.

- 10 -

Short Title: Impact of using Zinc Oxide versus Moist Exposed Wound Ointment (MEBO) in treatment of second stage pressure ulcer: A randomized control clinical trial.

Version: 5.0 (Dated 28-Mar-2023)

Effective date: 29-Mar-2023

Expiration date: 29-Mar-2024

Impact of using zinc oxide versus Moist Exposed Wound Ointment (MEBO) in treatment of second stage pressure ulcer: A randomized control clinical trial.

Study outcome measurement:

Data will be collected through one tool that will be collected by the assessor daily. It will include two sections as follows:

Section I: Patients' demographic data

This section was developed by the PI based on relevant literature. It will include demographic and medical history data will be collected from the patients' medical records without identifier such as age, sex, body mass index, history of smoking, diagnosis at the time of admission, and laboratory parameters including erythrocyte sedimentation rate (ESR) and C-reactive protein (CRP) will be recorded. Nutritional status of patients will be evaluated considering route of nutritional support (enteral or parenteral). Subject will be identify via serial codes.

Section II: Pressure ulcer assessment.

This section will be adopted from Bates-Jensen 2010 [31]. The Bates-Jensen Wound Assessment Tool (BWAT) will be used to evaluate wound healing. It is a validated wound assessment tool which is used in many healthcare settings for wound assessment. BWAT is straight forward to use and allows nurses to have an objective, comprehensive assessment of wounds. It consists of 13 items to evaluate wound size, type and depth, amount of necrotic tissue, amount and characteristics of exudate, the presence of granulation tissue, epithelialization, and peri- 6 wound skin. PU length and width was measured with a disposable ruler and expressed as cm². Patient will be examined daily till complete healing for the pressure ulcer and maximum one month. If the pressure ulcer not healed within the month of the treatment duration this patient will return to routine care of the hospital. If the any patient will be unable to continue the study because of death, discharge, or change in the care setting the researcher will be excluded from the study.

Each item is graded on a scale of 1 to 5, where a score of 1 indicates progress toward healing while a score of 5 indicates the absence of healing or wound deterioration. Cumulative BWAT scores vary

- 11 -

Short Title: Impact of using Zinc Oxide versus Moist Exposed Wound Ointment (MEBO) in treatment of second stage pressure ulcer: A randomized control clinical trial.

Version: 5.0 (Dated 28-Mar-2023)

Effective date: 29-Mar-2023

Expiration date: 29-Mar-2024

Impact of using zinc oxide versus Moist Exposed Wound Ointment (MEBO) in treatment of second stage pressure ulcer: A randomized control clinical trial.

from 13 to 65. The English version of BWAT has been reported to have good reliability (Cronbach alpha=0.91 and an interrater reliability coefficient of 0.99).

The ulcer status will be completed by the assessor when the pressure ulcer healed or the end of the month, the ulcers will be examined blindly and assessed as “Completely Healed,” “Partially Healed,” “Without Improvement,” or “Worsening.”. “**Completely healed**” was defined as an intact dermis and epidermis, and no abrasion or ulceration. “**Partially healed**” was defined as any decrease in ulcer size compared with the baseline ulcer tracing but excluding complete healing. “**Without improvement**” was defined as no change in ulcer size compared with the baseline ulcer tracing. “**Worsening**” was defined as any increase in ulcer size compared with the baseline ulcer tracing. Duration of treatment will be record at the assessment sheet.

Statistical Analysis Plan

Data obtained from the study will be coded and transformed into coding sheets. The results will be checked. Then, the data will be entered into SPSS system files (SPSS package version 22). Following data entry, checking and verification process will be carried out to avoid any errors during data entry. Finally, analysis and interpretation of data will be conducted. Categorical variables will be expressed as number and percentage while continuous variables will be expressed as mean and standard deviation.

Publication:

The results of this research will be published to either national or international publications. The main credit in publication will go to King Abdullah Medical City in Holy Capital and to the principal investigator and co-investigators. Others who have contributed less substantially will have an acknowledgement in the manuscript.

Ethical Part & Confidentiality:

- 12 -

Short Title: Impact of using Zinc Oxide versus Moist Exposed Wound Ointment (MEBO) in treatment of second stage pressure ulcer: A randomized control clinical trial.

Version: 5.0 (Dated 28-Mar-2023)

Effective date: 29-Mar-2023

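### Cheap gain in precision: pre-specify baseline ulcer size, which the protocol already records and ties to a 12-day healing difference, as a covariate

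*Protocol*

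**What the plan says.** **Prognosis.** The Study Procedure section of the protocol reports from a cited study that full re-epithelialisation of a stage II ulcer is slow ("it takes approximately 23 days") and that "On average, a small ulcer heals 12 days faster compared with those with a surface of 3.1 cm² or greater". Both figures serve to justify following patients for at most one month.

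**Data collected.** Under Study outcome measurement, ulcer length and width are measured by ruler and expressed in cm². The final healing categories are judged against a baseline tracing. BWAT, the measure for the primary objective, is scored daily, and treatment duration is recorded for the secondary objective of recovery time. A patient may have several ulcers: "If a patient has more than one ulcer, all the ulcers will be treated by the same method".

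**Analysis.** The Statistical Analysis Plan section lists numbers and percentages for categorical variables and means and standard deviations for continuous ones. It names no covariate and rules none out.

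**Size.** The sample size is 28 per group, then "in addition to attrition rate 20 % therefore sample size will be 34 patients for each group".

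**Allocation.** The Randomization section opens with "Simple randomization method will be used through electronic randomization" and continues "The randomization list was generated electronically through R using the Random Allocation Rule by research center member". Study Procedure repeats the Random Allocation Rule, with "the subject will be randomized using electronic randomization 1:1 ratio" and "Patients will equally be allocated into 2 groups randomly".

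**The concern.** Ulcer size is the only predictor of healing time that the protocol quantifies, and the 12-day gap is large beside the quoted 23 days. With about 28 evaluable patients per arm, any spread in the outcome that size could explain stays in the standard error if size is not used. The measurement already exists, so the precision would cost no patients and no visits. It must be claimed in advance, however, because a covariate chosen after outcomes are seen invites the charge of selection.

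The allocation wording is a separate and smaller matter. Simple randomisation assigns each patient independently and leaves the arm totals to chance, whereas the Random Allocation Rule fixes them. The two descriptions cannot both be true of one list.

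**Working it through.** **1. The plan's own sample size.** With p1 = 0.5, p2 = 0.167 and C = (0.84 + 1.96)² = 7.84:

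n = (0.5 × 0.5 + 0.167 × 0.833) × 7.84 / 0.333² = 27.51, rounded up to 28. Then 28 × 1.2 = 33.6, rounded up to 34 per group. The stated figures reproduce. Adjustment changes neither.

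**2. Inputs for the gain.**
- From the protocol: a 12-day gap, approximately 23 days overall, follow-up of one month (30 days used), 28 evaluable per arm.
- Assumed, because the protocol does not give them: within-group SD of healing time 8 to 20 days; share of large ulcers p from 0.3 to 0.7; two groups that cover all patients (the protocol does not define a small ulcer); 23 days read as a mean (the protocol does not call it one); gamma-distributed times for the capped and binary outcomes.

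**3. Uncapped healing time.** This needs only the gap, the SD and p:

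share explained = 144 p(1 − p) / [144 p(1 − p) + SD²]

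Example with p = 0.5 and SD = 12: 36 / (36 + 144) = 0.20.

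**4. Capped time and healing by day 30.** The group means are 23 − 12p (small) and 35 − 12p (large). For each group the gamma distribution gives the mean and variance of time capped at 30 days and the probability of healing by day 30. The share explained is the between-group variance divided by the total. Ranges are over p = 0.3, 0.5 and 0.7:

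| Within-group SD (days) | Uncapped time | Time capped at 30 days | Healed by day 30 |
|---|---|---|---|
| 8 | 0.321–0.360 | 0.305–0.401 | 0.079–0.223 |
| 12 | 0.174–0.200 | 0.194–0.260 | 0.058–0.115 |
| 15 | 0.118–0.138 | 0.154–0.207 | 0.047–0.081 |
| 20 | 0.070–0.083 | 0.119–0.159 | 0.037–0.054 |

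**5. In patients.** Equivalent n per arm = 28 / (1 − share), ignoring the one degree of freedom spent on the covariate:
- capped time: 28 / (1 − 0.119) = 31.8 up to 28 / (1 − 0.401) = 46.7
- healed by day 30: 28 / (1 − 0.037) = 29.1 up to 28 / (1 − 0.223) = 36.0

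**6. BWAT.** Adjusting a follow-up score for its baseline removes a share r² of its variance. The protocol gives no r. For illustration, r = 0.3, 0.5 or 0.7 would remove 9%, 25% or 49%.

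**7. Allocation wording.** With 68 patients, independent 1:1 assignment gives exactly 34:34 with probability C(68,34) / 2⁶⁸ = 0.096. The Random Allocation Rule gives it with certainty. Every statement except the word for simple randomisation fits the Rule.

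**The case against.** The strongest objection is that covariates are a standard item of a separate statistical analysis plan, which may exist and is not shown. That stands: their absence here is no fault, and if such a plan already names baseline size, nothing more is needed.

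It also stands that the size of the gain is uncertain. The SD and the share of large ulcers are undocumented, and at an SD of 20 days the benefit for healing by day 30 is only one or two patients per arm. The largest gains concern recovery time, which is the secondary objective. The model also implies about 72 to 77% healed by day 30, against planning proportions of 0.5 and 0.167. The protocol does not say which outcome those proportions describe, but if it is healing, the model does not match them. Nor is size wholly ignored, since BWAT scores it and the healing categories refer to the baseline tracing.

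Three stronger readings are tempting and are not supported:
- A reader might infer that unstratified allocation biases the result. It does not. With 34 per arm, the share of large ulcers would differ by 15 points or more in about 18% (30% large) to 22.5% (50% large) of trials, moving an unadjusted mean by 12 × 0.15 = 1.8 days or more. That is chance, already allowed for in the standard error.
- A reader might infer that adjustment lifts power to about 80%. Simulations reach 0.78–0.81, from 0.58–0.64, only for capped recovery time with SD 8 and an assumed 25% faster healing in one arm. With SD 12 the rise is from 0.34–0.37 to 0.42–0.44.
- A reader might infer from the simple-randomisation wording that the arm sizes are at risk. The rest of the text makes the intended method clear.

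**Conclusion.** This is a worthwhile improvement and not an error. The protocol cites a strong link between ulcer size and healing time, records size at baseline, and makes no use of it in its analysis section. The benefit is precision only. Under the assumptions listed it ranges from small (about 4% of the variance of healing by day 30, or 7% of uncapped healing time) to substantial (about 40% of the variance of capped time). No single figure can be defended from the protocol, and the effect on the BWAT comparison is unknown. The recommendation does not depend on the upper end, because it needs no new data.

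The allocation wording is a real inconsistency, but an editorial one: no sample size, estimate or conclusion changes.

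**What to change.** In the protocol or the statistical analysis plan, before outcome data are seen:

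- Name baseline area of one index ulcer per patient as a covariate in the recovery-time and healing comparisons, and baseline BWAT as a covariate in the BWAT comparison.
- Give the rule for choosing the index ulcer, and require the choice to be recorded before the allocation envelope is opened.
- State how area is obtained (ruler or tracing) and its form in the model: continuous, or split at 3.1 cm².
- If a logistic model is used, report a standardised difference in proportions, since the adjusted odds ratio answers a different question from the unadjusted one. If a Cox model is used, say likewise whether the conditional hazard ratio or a standardised contrast is reported.
- Delete the simple-randomisation phrase and name the Random Allocation Rule once.

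The cost is a few sentences. No extra patients, visits or measurements are needed, and the existing randomisation list stays in use. The downside is that the index-ulcer rule, the covariate form and the estimand must all be settled beforehand.

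### The sample size is calculated for two unlabelled proportions, while the measure named for the primary objective is the daily BWAT score

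*Protocol*

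**What the plan says.** Under Objective measures, the protocol gives one measure for the primary objective: "Wound healing will be assessed by using Bates–Jensen Wound Assessment Tool (BWAT) daily for both treatments". The secondary objective is recovery time. Study outcome measurement, Section II, repeats the choice ("The Bates-Jensen Wound Assessment Tool (BWAT) will be used to evaluate wound healing") and describes 13 items graded 1 to 5, with a total from 13 to 65. No cut-off is set on that total.

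The Sample Size calculation section uses a formula for comparing two proportions. The rates are defined only as "p1 and p2 = Proportion of two groups", and the constant C as "Standard value for the corresponding level of α and β selected for the study", with value (0.84+1.96)². The rates entered are 0.50 and 0.167. Their origin is given as "The sample size for the study calculated using the following formula based on the study of" one earlier published trial, without saying which of its results was used. The outcome is 28 per group, raised to 34 for 20% attrition.

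Study outcome measurement also defines a four-level ulcer status (completely healed, partially healed, without improvement, worsening): "The ulcer status will be completed by the assessor when the pressure ulcer healed or the end of the month". This status is not called primary and is not connected to the two rates.

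At the end of Significance of the study, the protocol says the trial is to "determine which one is superior to other".

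**The concern.** A sample size justifies a trial only for the endpoint it was calculated on. Here the named endpoint is a score measured repeatedly, and the calculation is for a yes/no event that the protocol does not identify. A score from 13 to 65 yields a proportion only after a threshold is chosen, and none is given.

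Two things are at stake:

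- **Which result decides.** BWAT and ulcer status can disagree. One ointment could give a lower mean BWAT while complete healing is similar in both arms. The protocol does not say which of these settles superiority, so the choice could be made after the data are seen.
- **What the trial can detect.** The only justification for 34 per group rests on an unidentified event. Nothing in the protocol supports 80% power for BWAT.

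**Working it through.** **Inputs from the protocol.** p1 = 0.50, p2 = 0.167, C = (0.84+1.96)² = 7.84, 20% attrition, 1:1 allocation. The 1.96 corresponds to two-sided alpha 0.05, and the 0.84 to 79.95% power. No BWAT SD, target difference or analysis day is given.

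**Step 1: reproduce the stated figure.**

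n = [p1(1−p1) + p2(1−p2)] × C / (p1−p2)²
= (0.25 + 0.1391) × 7.84 / 0.1109 = 27.51, rounded up to 28.

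Then 28 × 1.2 = 33.6, rounded up to 34. Both agree with the protocol. (The worked line as typed omits the brackets of the displayed formula and would literally give 10.1. With the brackets it gives 27.5.) The arithmetic is not the problem.

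**Step 2: what this buys for a proportion.** Power at 0.50 vs 0.167, and the difference detectable with 80% power by the protocol's formula:

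| Evaluable per arm | Power, protocol's formula | Power, exact enumeration of the uncorrected chi-square test | Detectable difference, up from 0.167 / down from 0.50 |
|---|---|---|---|
| 28 | 80.6% | 78.2% | 0.330 / 0.331 |
| 34 | 87.5% | 86.1% | 0.299 / 0.306 |

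So 80% power means a difference of about 33 points with 28 per arm, or 30 to 31 points if all 34 are evaluable, at these rates.

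**Step 3: what the same numbers buy for BWAT.** For a comparison of means on a single day, the difference detectable with 80% power, in SD units, is

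2.8 × √(2/n) × √(1−r²),

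where r is the correlation between baseline and outcome if the analysis adjusts for baseline (r = 0 means unadjusted). For example, with n = 28 and r = 0: 2.8 × √(2/28) = 0.748. The values r = 0.5 and 0.7 are assumptions, not protocol figures. Results are by normal approximation / noncentral t:

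| r | n = 28 | n = 34 |
|---|---|---|
| 0 | 0.748 / 0.762 | 0.679 / 0.690 |
| 0.5 (assumed) | 0.648 / 0.660 | 0.588 / 0.597 |
| 0.7 (assumed) | 0.534 / 0.545 | 0.485 / 0.493 |

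If the true BWAT difference were 0.5 SD (also an assumption), an unadjusted comparison with 28 per arm would have about 46% power, and 80% power would need 63 per arm. Without an SD, none of these can be turned into BWAT points.

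**Step 4: look for a link elsewhere in the protocol.**

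- The four-level status could supply a proportion, but more than one: completely healed, or any improvement. Neither is tied to p1 and p2.
- The cited trial cannot label the arms by itself, because the introduction says no earlier study compared these two ointments.
- Study Procedure cites the same trial for a one-week result, while patients here are followed for up to one month. The time point behind 0.50 and 0.167 is therefore open as well.

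**The case against.** The best defence is that the link is missing rather than the outcome wrong. Objective measures names an instrument and does not prescribe a comparison of mean scores. The ulcer status is described in the same part of the assessment tool as BWAT, is recorded at healing or at one month, and fits a two-proportion formula. The event and arm behind the rates may also be traceable in the cited trial. On this reading the sponsor meant complete healing and only failed to say so.

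Part of this stands. Complete healing is a plausible source, and it cannot be shown from the protocol that the rates fail to match it. It is also true that the BWAT figures above assume a single-day comparison. An analysis of the daily series could have different power, so they do not prove the trial underpowered.

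This does not remove the point. A reader would have to guess the event, the time and the arm, and would also have to override the one measure the protocol does name. For the BWAT score itself, power from a two-proportion formula has no bearing. Nor is this detail that could wait for a separate analysis plan, since the protocol itself fixes both the primary measure and the sample size. How the daily scores are summarised and whether baseline is adjusted for could be left to such a plan. The endpoint on which the trial is sized could not.

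**Conclusion.** The concern holds and must be fixed. The protocol's arithmetic is right, but it answers a question about an unidentified event and not about the named primary measure. The implied 80% power holds only for a difference of about 33 points between two proportions with 28 evaluable per arm. For BWAT, the planned size gives 80% power for about 0.75 SD with 28 per arm, or 0.68 SD with 34, unadjusted on a single day. With baseline adjustment at an assumed correlation of 0.5 to 0.7, the figures are about 0.65 to 0.53 SD with 28 and 0.59 to 0.49 SD with 34. Whether such differences are realistic cannot be judged from the protocol.

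**What to change.** Make the primary endpoint and the sample-size endpoint the same, in one of two ways.

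1. **Binary primary.** Name an outcome that is already recorded, for example complete healing by the end of the month. Count it per patient, because Study Procedure allows several ulcers in one patient. State the event, time point and arm from which 0.50 and 0.167 were taken, and keep them only if they describe that same event; otherwise replace them. Move BWAT to secondary. State that 28 evaluable per arm gives about 80% power only for a difference of about 33 points at those rates.
2. **BWAT primary.** Fix the analysis day and replace the two-proportion calculation with the detectable BWAT difference: about 0.75 SD with 28 per arm (0.68 SD with 34) unadjusted, or about 0.65 to 0.53 SD with 28 if adjusted for baseline at an assumed correlation of 0.5 to 0.7. Add a justified SD if the difference is to be read in BWAT points.

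The cost is a protocol amendment, tracing the planning rates to their source, and possibly a less favourable power figure. The first option changes which outcome is primary, so it is more than an edit of wording. Alignment itself needs no new data and no added patients. If the traced rates turn out to describe another event, the sponsor must replace them and then either recompute the sample size or restate the detectable difference at the planned 34 per group.
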